4.3 STUDY TREATMENT

Details on the therapeutic agents for each treatment arm are provided in the respective appendix for that treatment arm, as outlined in [Table 4](#).

4.3.1 Investigational Medicinal Product Handling and Accountability

The IMPs for this study are atezolizumab, tiragolumab, RO7247669, nivolumab, and ipilimumab. [Appendix 17](#) identifies all IMPs, non-investigational medicinal products, and auxiliary medicinal products for this study.

All IMPs required for completion of this study will be provided by the Sponsor where required by local regulations. The study site (i.e., investigator or other authorized personnel [e.g., pharmacist]) is responsible for maintaining records of IMP delivery to the site, IMP inventory at the site, IMP use by each patient, and disposition or return of unused IMP, thus enabling reconciliation of all IMP received, and for ensuring that patients are provided with doses specified by the protocol.

The study site should follow all instructions included with each shipment of IMP. The study site will acknowledge receipt of IMPs supplied by the Sponsor using the IxRS to confirm the shipment condition and content. Any damaged shipments will be replaced. The investigator or designee must confirm that appropriate temperature conditions have been maintained during transit for all IMPs received and that any discrepancies have been reported and resolved before use of the IMPs. All IMPs must be stored in a secure, environmentally controlled, and monitored (manual or automated) area in accordance with the labeled storage conditions, with access limited to the investigator and authorized staff.

Only patients enrolled in the study may receive IMPs, and only authorized staff may supply or administer IMPs.

IMPs will either be disposed of at the study site according to the study site's institutional standard operating procedure or will be returned to the Sponsor (if supplied by the Sponsor) with the appropriate documentation. The site's method of destroying Sponsor-supplied IMPs must be agreed to by the Sponsor. The site must obtain written authorization from the Sponsor before any Sponsor-supplied IMP is destroyed, and IMP destruction must be documented on the appropriate form.

Accurate records of all IMPs received at, dispensed from, returned to, and disposed of by the study site should be recorded on a drug accountability log.

Refer to the pharmacy manual and/or the applicable Investigator's Brochure for information on IMP handling, including preparation and storage, and accountability.

4.3.2 Post-Trial Access to Study Treatment

Currently, the Sponsor does not have any plans to provide study treatments or interventions to patients who have completed the study. The Sponsor may evaluate whether to continue providing study treatments in accordance with the Roche Global Policy on Continued Access to Investigational Medicinal Product, available at the following website:

http://www.roche.com/policy_continued_access_to_investigational_medicines.pdf

4.4 CONCOMITANT THERAPY AND PROHIBITED FOOD

Details on concomitant therapy, prohibited food, and additional restrictions are provided in the respective appendix for each treatment arm (see Sections [A11–4.2](#) [Nivo + Ipi], [A12–4.2](#) [RO7247669 2100 mg], [A13–4.2](#) [Atezo + Tira], and [A14–4.2](#) [RO7247669 2100 mg + Tira Cohorts 1 and 2], [A15–4.2](#) [RO7247669 600 mg], and [A16–4.2](#) [RO7247669 600 mg + Tira]).

4.5 STUDY ASSESSMENTS

A schedule of activities to be performed during the study is provided for screening in [Appendix 10](#) and for each treatment arm in Sections [A11–6](#) (Nivo + Ipi), [A12–6](#) (RO7247669 2100 mg), [A13–6](#) (Atezo + Tira), [A14–6](#) (RO7247669 2100 mg + Tira Cohort 1), and [A14–8](#) (RO7247669 2100 mg + Tira Cohort 2), [A15–6](#) (RO7247669 600 mg), and [A16–6](#) (RO7247669 600 mg + Tira). All activities must be performed and documented for each patient. Patients will be closely monitored for safety and tolerability throughout the study. Patients should be assessed for toxicity prior to each infusion; dosing will occur only if the clinical assessment and local laboratory test values are acceptable.

4.5.1 Informed Consent Forms and Screening Log

Written informed consent for participation in the study must be obtained before performing any study-related procedures (including screening evaluations) and may be obtained more than 28 days before initiation of study treatment. Informed Consent Forms for enrolled patients and for patients who are not subsequently enrolled will be maintained at the study site.

Screening evaluations are to be performed within 28 days prior to initiation of study treatment (Day 1). All screening evaluations must be completed and reviewed to confirm that patients meet all eligibility criteria before enrollment.

Patients who fail their first screening for study eligibility may qualify for two re-screening opportunities (for a total of three screenings per patient) at the investigator's discretion. Patients must re-sign the Informed Consent Form prior to re-screening.

Results of standard-of-care tests or examinations performed prior to obtaining informed consent and within a specified time prior to Day 1 may be used as outlined in the schedule of activities (see [Appendix 10](#) [screening], Sections [A11–6](#) [Nivo + Ipi], [A12–6](#) [RO7247669 2100 mg], [A13–6](#) [Atezo + Tira], [A14–6](#) [RO7247669 2100 mg + Tira Cohort 1], [A14–8](#) [RO7247669 2100 mg + Tira Cohort 2], [A15–6](#) [RO7247669 600 mg], and [A16–6](#) [RO7247669 600 mg + Tira]). Such tests do not need to be repeated for screening or re-screening.

4.5.2 Medical History, Molecular Profile, Concomitant Medication, and Demographic Data

Medical history, including clinically significant diseases, surgeries, cancer history (including prior cancer therapies and procedures), reproductive status, and smoking history, will be recorded at baseline. The patient's molecular profile for melanoma, if available, will be recorded at screening and whenever updated information becomes available during the study. In addition, all medications (e.g., prescription drugs, over-the-counter drugs, vaccines, herbal or homeopathic remedies, nutritional supplements) used by the patient within a specified time prior to initiation of study treatment will be recorded. At the time of each follow-up physical examination, an interval medical history should be obtained and any changes in medications and allergies should be recorded. Demographic data will include age, sex, and self-reported race/ethnicity.

Refer to the schedule of activities for information about the timing of medical history, molecular profile, concomitant medication, and demographic data collection ([Appendix 10](#) [screening], Sections [A11–6](#) [Nivo + Ipi], [A12–6](#) [RO7247669 2100 mg], [A13–6](#) [Atezo + Tira], [A14–6](#) [RO7247669 2100 mg + Tira Cohort 1], [A14–8](#) [RO7247669 2100 mg + Tira Cohort 2], [A15–6](#) [RO7247669 600 mg], and [A16–6](#) [RO7247669 600 mg + Tira]).

4.5.3 Physical Examinations

A complete physical examination, performed at screening and other specified visits, should include evaluations as per clinical practice (e.g., evaluations of the head, eyes, ears, nose, and throat, and the cardiovascular, dermatologic, musculoskeletal, respiratory, gastrointestinal, genitourinary, and neurologic systems). Any abnormality identified at baseline should be recorded on the General Medical History and Baseline Conditions electronic Case Report Form (eCRF).

Limited, symptom-directed physical examinations should be performed at specified post-baseline visits and as clinically indicated. Changes from baseline abnormalities should be recorded in patient notes.

New or worsened clinically significant abnormalities should be recorded as adverse events on the Adverse Event eCRF.

Height will be recorded at screening. Weight will be recorded at specified timepoints during the study.

Refer to the schedule of activities for information about the timing of physical examinations ([Appendix 10](#) [screening], Sections [A11–6](#) [Nivo + Ipi], [A12–6](#) [RO7247669 2100 mg], [A13–6](#) [Atezo + Tira], [A14–6](#) [RO7247669 2100 mg + Tira Cohort 1], [A14–8](#) [RO7247669 2100 mg + Tira Cohort 2], [A15–6](#) [RO7247669 600 mg], and [A16–6](#) [RO7247669 600 mg + Tira]).

4.5.4 Vital Signs

Vital signs will include measurements of respiratory rate, pulse rate, and systolic and diastolic blood pressure while the patient is in a seated position, pulse oximetry, and temperature.

Vital signs should be measured within 60 minutes prior to administration of each study treatment and, if clinically indicated, during or after treatment administration. In addition, vital signs should be measured at other specified timepoints as outlined in the schedule of activities (see [Appendix 10](#) [screening], Sections [A11–6](#) [Nivo+Ipi], [A12–6](#) [RO7247669 2100 mg], [A13–6](#) [Atezo+Tira], [A14–6](#) [RO7247669 2100 mg+Tira Cohort 1], [A14–8](#) [RO7247669 2100 mg+Tira Cohort 2], [A15–6](#) [RO7247669 600 mg], and [A16–6](#) [RO7247669 600 mg+Tira]).

Any abnormality identified at baseline should be recorded on the General Medical History and Baseline Conditions eCRF. New or worsened clinically significant abnormalities should be recorded as adverse events on the Adverse Event eCRF.

4.5.5 Electrocardiograms

An ECG will be performed at screening, as clinically indicated, and as outlined in the schedules of activities (see [Appendix 10](#) [screening], Sections [A11–6](#) [Nivo+Ipi], [A12–6](#) [RO7247669 2100 mg], [A13–6](#) [Atezo+Tira], [A14–6](#) [RO7247669 2100 mg+Tira Cohort 1], [A14–8](#) [RO7247669 2100 mg+Tira Cohort 2], [A15–6](#) [RO7247669 600 mg], and [A16–6](#) [RO7247669 600 mg+Tira]). ECGs for each patient should be obtained from the same machine wherever possible. Lead placement should be as consistent as possible. It is recommended that patients be resting in a supine position for at least 10 minutes prior to ECG recording.

For safety monitoring purposes, the investigator must review, sign, and date all ECG tracings. Paper copies of ECG tracings will be kept as part of the patient's permanent study file at the site. Any morphologic waveform changes or other ECG abnormalities must be documented on the eCRF.

4.5.6 Evaluation of Left Ventricular Function

Patients will undergo evaluation of LVEF, either by TTE or MUGA scan at screening and as outlined in the schedules of activities (see [Appendix 10](#) [screening], Sections [A11–6](#) [Nivo+Ipi], [A12–6](#) [RO7247669 2100 mg], [A13–6](#) [Atezo+Tira], [A14–6](#) [RO7247669 2100 mg+Tira Cohort 1], [A14–8](#) [RO7247669 2100 mg+Tira Cohort 2], [A15–6](#) [RO7247669 600 mg], and [A16–6](#) [RO7247669 600 mg+Tira]). Evaluation of LVEF must be performed using the same method for each patient. TTE measurements should be performed by the same operator whenever possible, following the most recent echocardiography society guidelines. Paper copies of reports will be kept as part of the patient's permanent study file at the site.

4.5.7 Tumor and Response Evaluations

4.5.7.1 Radiographic Procedures for Screening (Cohorts 1 and 2)

All measurable and evaluable lesions should be assessed and documented at screening as outlined in the schedule of activities ([Appendix 10](#)). Tumor assessments performed as standard of care prior to obtaining informed consent and within 28 days prior to randomization/enrollment do not have to be repeated at screening.

Screening assessments must include CT scans (with oral and/or IV contrast) or magnetic resonance imaging (MRI) scans of the chest, abdomen, and pelvis. A spiral CT scan of the chest may be obtained but is not a requirement. If a CT scan with contrast is contraindicated (i.e., in patients with contrast allergy or impaired renal clearance), a non-contrast CT scan of the chest may be performed and MRI scans of the abdomen and pelvis should be performed. A CT scan with contrast or MRI scan of the head with contrast must be done at screening to evaluate CNS metastasis in all patients (MRI scan must be performed if contrast is contraindicated). Bone scans and CT or MRI scans of the neck should also be performed if clinically indicated. At the investigator's discretion, other methods of assessment of measurable disease may be used as per RECIST v1.1.

If a CT scan for tumor assessment is performed in a positron emission tomography (PET)/CT scanner, the CT acquisition must be consistent with the standards for a full-contrast diagnostic CT scan. The same radiographic procedures used to assess disease sites at screening should be used for subsequent tumor assessments (e.g., the same contrast protocol for CT scans).

All measurable and/or evaluable lesions identified at baseline should be re-assessed at subsequent tumor evaluations as outlined in Section [4.5.7.2](#) (Cohort 1) or Section [4.5.7.3](#) (Cohort 2). The same radiographic procedures used to assess disease sites at screening should be used for subsequent tumor assessments (e.g., the same contrast protocol for CT scans).

4.5.7.2 Cohort 1 Tumor, Response, and Disease Status Evaluations

Patients in Cohort 1 will be assessed for pathologic and radiologic response to treatment. Patients will undergo pathological tumor assessments after 6 weeks of treatment at surgery (CLND). The complete resection of Stage III lymph nodes (CLND) in Week 7 must be performed in compliance with the criteria for adequate surgical procedures for therapeutic lymph node dissection (see [Appendix 4](#)). CLND should be performed as planned if the patient is receiving corticosteroids or other anti-inflammatory drugs for the management of immune-mediated adverse events, provided these are being given at a stable or tapering dose and the severity of adverse events is Grade 2 or better. CLND may be delayed for up to 2 weeks if study treatment-related adverse events have not improved sufficiently at the time of planned surgery (see Section [3.1.3](#)). Pathological response will be determined by local and independent pathologic review according to INMC guidelines (Tetzlaff et al. 2018; [Appendix 3](#)).

Patients will undergo radiographic tumor assessments at baseline and after 6 weeks of treatment before surgery (CLND) according to RECIST v1.1, as outlined for each arm in the schedules of activities (see Sections [A11–6](#) [Nivo + Ipi], [A12–6](#) [RO7247669 2100 mg], [A13–6](#) [Atezo + Tira], [A14–6](#) [RO7247669 2100 mg + Tira Cohort 1], [A15–6](#) [RO7247669 600 mg], and [A16–6](#) [RO7247669 600 mg + Tira]). At the treatment completion/discontinuation visit (Week 13), the disease status will be assessed by radiographic tumor assessments for the absence of recurrent disease. *Tumor assessments that have been performed outside the protocol-mandated time window do not have to be repeated. However, at the investigator's discretion, tumor assessments may be repeated at any time if progressive disease is suspected.*

Overall response at a single timepoint will be assessed by the investigator using RECIST v1.1 (see [Appendix 1](#)). Assessments should be performed by the same evaluator, if possible, to ensure internal consistency across visits. Available results must be reviewed by the investigator prior to treatment administration.

Disease Follow-Up and Confirmation of Disease Progression or Recurrence

During the neoadjuvant treatment, diagnosis of disease progression should be confirmed by clinical, laboratory, radiological, and/or histological findings. After surgery, prior to commencing adjuvant treatment or observation, the first planned tumor assessment will be performed in Week 13 to conclude the neoadjuvant therapy-surgery intervention window and should include a CT scan. After the treatment phase, during the follow-up phase, all patients must be followed to assess disease recurrence and survival as outlined for each arm in the schedules of activities (see Sections [A11–6](#) [Nivo + Ipi], [A12–6](#) [RO7247669 2100 mg], [A13–6](#) [Atezo + Tira], [A14–6](#) [RO7247669 2100 mg + Tira Cohort 1], [A15–6](#) [RO7247669 600 mg], and [A16–6](#) [RO7247669 600 mg + Tira]). *Tumor assessments that have been performed outside the protocol-mandated time window do not have to be repeated. However, at the investigator's discretion, tumor assessments may be repeated at any time if progressive disease is suspected.*

The designation of disease recurrence, whether local, regional, or distant, can be made only when clinical, laboratory, radiological and/or histological findings confirm the diagnosis.

During the post-surgery period, disease status should be clinically evaluated and documented every 3 months for the first 2 years; every 6 months in the third year and annually thereafter until a diagnosis of a recurrence (defined below). In addition to physical examinations, liver function tests, bone scans, chest X-ray/diagnostic CT scan, liver imaging, and/or other radiographic modalities may be considered when clinically indicated to exclude metastatic disease within timelines as per current local standard of practice.

The diagnosis of a progression or recurrence should be confirmed histologically whenever clinically possible. The earliest date of diagnosis of disease progression or

recurrent disease should be used and recorded. This date should be based on objective clinical, radiological, histological, or cytological evidence. Recurrent disease includes local, regional, or distant recurrence: local recurrence is defined as tumor regrowth within 2 cm of the primary lesion's tumor bed; regional recurrence as any nodal or non-nodal tumor lesions that are more than 2 cm from the primary lesion but are not beyond the regional nodal basin; distant recurrence as any non-local/non-regional recurrence.

The definitions of and procedures for confirming disease recurrence, death, and other noteworthy events on follow-up are provided below. Documentation of recurrence will require specification of all sites involved to establish the pattern of recurrence.

The following criteria of treatment failure constitute the only acceptable evidence of disease recurrence:

- Lung: Positive cytology or biopsy in the presence of a single new lesion or the appearance of multiple lesions consistent with metastatic disease
- Liver: Positive cytology or biopsy in the presence of a single new lesion or the appearance of multiple lesions consistent with metastatic disease
- Central nervous system: A positive brain CT or MRI scan or CSF cytology
- Cutaneous, subcutaneous, and lymph node recurrence: Positive cytology or biopsy in the presence of a single new lesion or the appearance of multiple lesions consistent with metastatic disease
- Bone and other organs: Positive cytology or biopsy in the presence of a single new lesion or the appearance of multiple lesions consistent with metastatic disease identified on two different radiologic studies (i.e., positive nuclear bone scan or PET scan and contrast GI series or ultrasound, X-ray or CT of abdomen for abdominal disease)

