6.4 EFFICACY ANALYSES

6.4.1 Primary Efficacy Endpoint in Cohort 1

The primary efficacy endpoint in Cohort 1 is pRR at time of surgery. pRR will be assessed after completion of neoadjuvant treatment (Week 7) at time of CLND.

The pRR is defined as the proportion of patients who achieve pCR (a complete absence of viable tumor in the treated tumor bed), pathologic near complete response (pnCR; <10% of viable tumor in the treated tumor bed); and pathologic partial response (pPR; <50% of the treated tumor bed is occupied by viable tumor cells) as determined by independent pathologic review. Patients with missing or no pathologic response assessment, *including patients who do not proceed to CLND*, will be classified as non-responders.

pRR will be calculated for each arm along with 95% CIs (Clopper-Pearson method). The difference in pRR between the experimental arms and the control arm will also be calculated, along with 95% CIs using the Wald method with continuity correction.

6.4.2 Secondary Efficacy Endpoints in Cohort 1

The secondary efficacy endpoints in Cohort 1 are pRR at time of surgery as determined by local pathologic assessment, event-free survival (EFS), RFS, OS, and ORR prior to surgery. pRR is defined in Section [6.4.1](#).

EFS is defined as the time from randomization to any of the following events (whichever occurs first): disease progression that precludes surgery, as assessed by the investigator according to RECIST v1.1 (see Section [4.5.7](#)); local, regional, or distant disease recurrence; or death from any cause. Patients who have not experienced such events will be censored at the time of their last post-tumor tumor assessment.

RFS is defined as the time from surgery to the first documented recurrence of disease or death from any cause. For patients who do not have documented recurrence of disease or death, RFS will be censored at the day of the last tumor assessment.

OS is defined as the time from randomization to death from any cause. Patients who are still alive at the time of OS analysis will be censored at the last date they were known to be alive.

The Kaplan-Meier method will be used to estimate the median for RFS, EFS, and OS, 95% CIs will be constructed using the Brookmeyer and Crowley method. The RFS, EFS, and OS rate at specific timepoints will also be estimated using the Kaplan-Meier method, with 95% CIs calculated on the basis of Greenwood's estimate for the variance.

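### Section 4.5.7.2 gives conflicting rules on whether a single new non-CNS lesion that cannot be biopsied is a recurrence, and Section 6.4.2 does not say how it is counted or dated for RFS and EFS

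*Combined protocol and SAP*

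**What the plan says.** Section 4.5.7.2 treats recurrence after surgery in two places.

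**The paragraphs on disease follow-up and confirmation.**
- A designation of recurrence "can be made only when clinical, laboratory, radiological and/or histological findings confirm the diagnosis".
- On tissue: "The diagnosis of a progression or recurrence should be confirmed histologically whenever clinically possible".
- The date rule begins "The earliest date of diagnosis of disease progression or" and goes on to cover recurrent disease. Clinical or radiological evidence is enough to support that date, as is histology or cytology.
- Clinical follow-up continues until recurrence, which these paragraphs say is defined further down.

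**The site list that closes the section.**
- It is introduced as exclusive: "The following criteria of treatment failure constitute the only acceptable evidence of disease recurrence".
- The first entry shows how a solitary lesion is handled: "Lung: Positive cytology or biopsy in the presence of a single new lesion or the appearance of multiple lesions consistent with metastatic disease". The same rule is given for liver, and for skin, subcutaneous and nodal sites.
- Bone and other organs carry it too, with an added imaging condition: "identified on two different radiologic studies".
- The CNS is the exception: "Central nervous system: A positive brain CT or MRI scan or CSF cytology".

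**Section 6.4.2.** "RFS is defined as the time from surgery to the first documented recurrence of disease or death from any cause". Without either, RFS is censored at the last tumor assessment. EFS takes recurrence as one of its components. Its pre-surgery component is investigator-assessed progression under RECIST v1.1 that precludes surgery. The section has no rule for a solitary lesion without tissue. Starting treatment for recurrence is neither an event nor a reason for censoring.

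**The concern.** When a solitary lesion outside the CNS cannot be sampled, the follow-up paragraphs let the investigator diagnose and date a recurrence, and the list does not. Two sites, or a site and a programmer, could handle the same patient differently and each cite Section 4.5.7.2.

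On the strict reading the error has one direction. A patient judged clinically to have relapsed, and perhaps already treated for it, stays event-free in RFS and EFS or is censored at the last scan, so both curves look better than they should. Because the study is open-label and the decision to biopsy is local, whether a relapse counts can depend on site practice. At stake are two secondary endpoints and the exploratory landmark rates at 1, 2, 3 and 5 years.

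**Working it through.** **Step 1. The two rules side by side, for one new lesion after surgery with no tissue obtainable.**

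| Question | Follow-up paragraphs | Site list |
|---|---|---|
| Is tissue required? | Only where feasible | Yes, at every site except the CNS |
| Can imaging alone qualify a solitary lesion? | Yes, through the and/or wording | Only in the CNS |
| Can multiple lesions qualify without tissue? | Yes | Yes; bone and other organs also need two imaging studies |
| Which date applies? | Earliest diagnosis, on objective evidence that may be radiological | Not stated |

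The rows on tissue and on imaging alone cannot both be followed for a solitary non-CNS lesion.

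**Step 2. A hypothetical patient, months counted from surgery.** A solitary lung lesion is seen at Month 9 and is larger at Month 12. Biopsy is not possible, treatment for recurrence starts, and a second lesion appears at Month 18.
- Follow-up paragraphs: event at Month 9.
- Site list: the recurrence qualifies at Month 18. With the earliest-date rule it may be dated back to Month 9; without it, Month 18.
- Site list, if no second lesion or positive tissue ever appears: no event unless the patient dies, and otherwise censoring at the last tumor assessment.

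Month 9 against Month 18 changes the 1-year landmark but not the 2-year one. The never-qualified case changes every later landmark.

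**Step 3. Illustrative size.** Section 6.1 sets no power or type I error target, and the plan states no event count, so there is no figure of the plan's to reproduce. Inputs:
- r, the proportion recurring: 20% (Section 3.4.4 cites durable RFS above 80%) or 40% (Section 1.1.2, relapse within 3 years of surgery).
- n = 40, within the 20–60 per experimental arm in Section 6.1.
- f, the share of recurrences that are solitary, non-CNS and never qualify: **not in the documents**; assumed 5%, 10% or 20%.

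Apparent RFS = 1 − r(1 − f). Shift = r × f. Patients affected = n × r × f.

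| r | f | True RFS | Apparent RFS | Shift (points) | Affected of 40 |
|---|---|---|---|---|---|
| 20% | 5% | 80% | 81% | 1 | 0.4 |
| 20% | 10% | 80% | 82% | 2 | 0.8 |
| 20% | 20% | 80% | 84% | 4 | 1.6 |
| 40% | 5% | 60% | 62% | 2 | 0.8 |
| 40% | 10% | 60% | 64% | 4 | 1.6 |
| 40% | 20% | 60% | 68% | 8 | 3.2 |

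f can also be built from two assumed parts: 30–60% of first recurrences solitary and non-CNS, and 10–40% of those without tissue. Then f runs from 0.30 × 0.10 = 3% to 0.60 × 0.40 = 24%. At r = 20% there are 40 × 0.20 = 8 events, of which 0.24 to 1.92 are affected, or 0.6 to 4.8 points. Taking f = 24% to r = 40% would give 0.40 × 0.24 = 9.6 points, the extreme corner of these assumptions.

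All of these are upper bounds for the assumed f. They treat every affected event as never counted, whereas later tissue, further lesions or death would turn some into events.

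**Step 4. Against precision.** The approximate 95% half-width is 1.96 × √(p(1 − p)/n). At n = 40 it is 12.4 points for p = 0.80 and 15.2 points for p = 0.60.

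**The case against.** The strongest reply is that the two texts can be read together. The follow-up paragraphs defer to a definition given further down. So the list decides what qualifies, and the request for histology adds tissue confirmation where the list does not demand it, as with multiple lesions. That reading is available. But it is the strict reading, so it removes the conflict only by leaving the unbiopsied solitary lesion uncounted, and Section 6.4.2 does not say that this is intended.

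Requiring tissue also protects specificity. Section 3.4.2 reports that, in some responding patients with apparent progression, biopsies of new or growing lesions found immune infiltrate without viable tumor. This stands, and it argues against making growth on imaging, or start of treatment, the main definition.

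The consequence is limited. RFS and EFS are secondary, no between-arm test of them is planned, the landmark rates are exploratory, and the same rule applies in every arm. Nothing in the documents shows a differential bias. The shifts in Step 3 are smaller than the half-widths in Step 4, although a confidence interval does not reveal a bias.

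A reader might infer more than the text supports:
- *That such lesions are definitely not events.* This is one reading; the and/or sentence and the radiological date rule support counting them.
- *That only more lesions or death can change the status.* Later positive cytology or biopsy also qualifies the recurrence.
- *That the event in Step 2 necessarily moves by 9 months.* The earliest-date rule may bring it back to Month 9.
- *That all of EFS is affected.* Before surgery EFS follows RECIST v1.1, and Appendix 1 treats a new malignant lesion as progression with no biopsy condition stated.

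**Conclusion.** The conflict is real and sits within one section. It concerns a single new non-CNS lesion after surgery without tissue. On the strict reading the patient has no RFS event, and no recurrence event for EFS, until positive tissue, further qualifying lesions or death. Otherwise the patient is censored at the last tumor assessment, even if treated for recurrence. The date of an event that qualifies later is a second open question.

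The direction is toward better RFS and EFS. The size cannot be taken from the documents. As upper bounds under assumed shares it is about 1 to 5 points at 20% recurrence, and 2 to 8 points at 40% with f between 5% and 20%. pRR and the pre-surgery part of EFS are untouched, so this is a correction worth making to secondary endpoints and not a threat to the primary analysis.

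Section 4.5.7.2 also refers to the arm-specific schedules of activities. These were not in the text available for this check, so a clarifying rule there cannot be excluded.

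**What to change.** 1. Reconcile the follow-up paragraphs of Section 4.5.7.2 with its site list, so that both give the same answer for a solitary non-CNS lesion without tissue.
2. State in Section 6.4.2 one rule for whether such a lesion counts for RFS and for the recurrence component of EFS, and how it is dated. Apply the date of earliest objective evidence to any event that qualifies later.
3. Record on the eCRF the evidence behind each recurrence: histology or cytology, multiple lesions, or imaging only.
4. Report RFS and EFS both ways. The narrow version counts tissue-confirmed or multiple-lesion events (with CNS events as now defined). The broad version adds imaging-only solitary lesions that grew or were treated as recurrence, dated at first imaging. New anti-cancer therapy is already collected about every 3 months (Sections 3.3 and 4.6.1), which helps identify the treated cases.

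Cost: a short text change, one eCRF field and one extra analysis. The broad version may include some false-positive solitary lesions; showing it beside the narrow version makes the effect visible. If the evidence type is not recorded prospectively, these cases may not be reliably separable later.
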